2. SYNOPSIS

PRODUCT NAME/NUMBER	HP-5000 Topical Patch
PROTOCOL NUMBER	HP-5000-US-05
DEVELOPMENT PHASE	2
PROTOCOL TITLE	A 4-week, randomized, double-blind, multicenter, placebo-controlled phase 2 study to evaluate the efficacy and safety of HP-5000 in subjects with osteoarthritis (OA) of the knee.
INDICATION	Osteoarthritis pain of the knee
OBJECTIVES	
Primary:
 
• To evaluate the efficacy of HP-5000 in subjects with osteoarthritis of the knee compared to placebo. 
Secondary:
 
• To evaluate the skin irritation, discomfort, adhesion, and adhesive residue following administration of HP-5000.• To evaluate the safety and tolerability of HP-5000.• To determine the plasma concentrations of diclofenac following administration of HP-5000.
STUDY DESIGN	
This is a multicenter, randomized, double-blind, and placebo-controlled phase 2 study evaluating 2 active formulations of HP-5000 in subjects with OA of the knee.
 
The study will consist of up to a 28-day Screening Phase that will include a Washout Period of current prescription and over the counter (OTC) analgesics, a 4-week Double-blind Treatment Phase, and a 1-week safety Follow-up Period.
 
Subjects will be seen in the clinic at the Screening Visit, Baseline Visit (Day 0), Day 7, Day 14, Day 28 (end of study), and Day 35 (safety Follow-up Visit). A \pm 2 days window will be allowed for all clinic visits during the Double-blind Treatment Phase and safety Follow-up visit. Site personnel will also contact the subjects by phone after the Screening Visit in order to instruct subjects on when to begin the Washout Period.
 
Screening Phase/Washout Period: Subjects will be seen in the clinic, and the study will be described to them. Subjects will be asked to sign the informed consent form. No screening procedures may begin prior to obtaining informed consent. After obtaining a written informed consent, subjects will be screened for participation in the study. Subjects whose preliminary entry criteria have been met will be contacted by the site via telephone starting from Day -25 and will be instructed to begin the Washout Period for 7 to 14 days, or at least 5 half-lives, whichever is longer, prior to the Baseline Visit (Day 0). During the Washout Period, rescue medication (acetaminophen [APAP]) will be permitted (a maximum of 2 g/day) except within 2 calendar days prior to the Baseline Visit (i.e., rescue medication is prohibited for 2 days until clinic visit on Day 0). During the Washout Period, subjects will complete daily electronic diaries (eDiaries) to record pain severity of their target knee and rescue medication usage from the day of Screening Visit to the day of the Baseline Visit.
 
Double-blind Treatment Phase: Following completion of the Screening/Washout Period, subjects will return to the clinic for their Baseline Visit (Day 0 or V2). Eligible subjects will be randomized to either HP-5000 [REDACTED], HP-5000 [REDACTED], or placebo in a 1:1:2 ratio. Subjects will apply a single patch to the target knee once [REDACTED] starting from Day 1 of the Double-blind Treatment Phase [REDACTED]. The patch will be removed [REDACTED] after application, and a

	
(WOMAC) pain score of [REDACTED] at the Baseline Visit (V2).
 
6. If female:
 
Subject is not breastfeeding or pregnant as confirmed by a negative pregnancy test at or within 48 hours of the Screening Visit. Women of child-bearing potential must use an acceptable method of contraception (including oral contraceptives, hormone implant, intrauterine device, and spermicide with barrier method, or male sexual partner[s] surgically sterile).Subject could not become pregnant because she is surgically sterile (hysterectomy or tubal ligation), confirmed to be postmenopausal (having amenorrhea for ≥ 12 months), or has had a hysterectomy with or without bilateral oophorectomy at least 6 months prior to the Screening Visit. 
7. Able to swallow and tolerate rescue medication, APAP (moderately sized tablets).
 
8. Be reliable, willing, and able to cooperate with all study procedures including the following:
 
Accurately fill out the eDiary on a daily basis.Return for study visits on the required dates.Accurately and reliably report symptoms (including treatment-emergent signs and symptoms).Use the patch as required by protocol.
--	---

Exclusion criteria:

1. Body mass index (BMI) > 40 .
2. The non-target knee pain severity score is [REDACTED] at Screening and Baseline (Day 0).
3. Any subject who disobeyed the restriction of prohibited therapies (i.e., use rescue medication) during Screening prior to the start of the Washout Period and 2 days prior to the Baseline Visit (V2).
4. Secondary OA of the knee (rheumatoid arthritis, gout, psoriasis, syphilitic neuropathy, ochronosis, metabolic or other primary bone disease or acute trauma).
5. Clinically significant elevation of serum creatinine (176.8 $\mu\text{mol/L}$), aspartate aminotransferase (AST) or alanine aminotransferase (ALT) (3 x upper limit of normal [ULN]) at the Screening Visit.
6. Known allergy or hypersensitivity to the use of diclofenac, [REDACTED], [REDACTED], ethanol, acetylsalicylic acid (aspirin [ASA]), or any other NSAID.
7. Severe uncontrolled cardiac, renal, hepatic or other systemic disease.
8. A documented gastroduodenal ulcer (upper GI series or endoscopy) or any GI bleeding (except hemorrhoidal) within 6 months prior to Screening Visit.
9. Documented history of alcohol or drug abuse within 1 year prior to study entry or positive alcohol/drug screen findings at Screening or Baseline.
10. Presence of chondrocalcinosis on X-ray if associated with a history of pseudogout or inflammatory flare-ups.
11. MAJOR SURGERY: Previous damage or surgery to the target knee at any time (i.e., damage/reconstruction of the anterior or posterior cruciate ligaments).
12. MINOR SURGERY on the target knee defined as anything other than major surgery (as defined above) within 1 year before study enrollment.
13. Treatment with oral or intra-muscular corticosteroids within 90 days of Screening Visit, treatment of the target knee with topical or intra-articular corticosteroids within 90 days of Screening Visit, or topical or intra-articular corticosteroid treatment of any other joint within 30 days of Screening (see **Section 9.10.2**).
14. Any subject who had received intra-articular viscosupplementation (e.g., Synvisc[®]) in the target knee 90 days prior to Screening Visit.
15. Any subject who had used opioids 7 days prior to the Screening Visit.
16. Any subject who had previous exposure to HP-5000.
17. Any subject whose participation would conflict with contraindications, warnings

	
or precautions as stated in the prescribing information for oral or topical diclofenac (e.g., any subject taking ACE inhibitors, cyclosporine, diuretics, lithium, or methotrexate – refer Section 3.1.5 of the Investigator Brochure (IB) for prescribing information).
 
18. Use of another investigational drug within 30 days prior to study entry.
 
19. Any subject with resolved, ongoing, or pending litigation or disability related to any health-related cause.
 
20. Any subject with fibromyalgia.
 
21. Any other painful or disabling conditions affecting the knee or leg.
 
22. Any skin abnormality present at the potential patch application site that is likely to be aggravated by the study drug (i.e., infection, rash, excessive fragility or dryness, any cut or abrasion), presence of tattoo, excessive hair or open sores, or scar tissue. Presence of significant skin disorder such as atrophy, psoriasis, or vitiligo.
 
23. Any subject expecting to have knee replacement surgery within 6 months.
 
24. Any subject with a psychiatric condition in the investigator's opinion may interfere with subject's participation in the study.
 
25. The subject is an employee, or family member of an employee, of the study center, the contract research organization (CRO) or the sponsor involved in this study.
								
INVESTIGATIONAL PRODUCTS	HP-5000 [REDACTED] topical patch HP-5000 [REDACTED] topical patch Each formulation contains [REDACTED] diclofenac sodium.								
REFERENCE PRODUCT	Placebo [REDACTED] : Patches identical in appearance to both HP-5000 [REDACTED] patch and HP-5000 [REDACTED] patch but without the active ingredient diclofenac sodium.								
TREATMENT REGIMENS	
The following are the different treatment arms:
 

Treatment Arm	Treatment	

HP-5000 [REDACTED]	One patch applied [REDACTED] to alternate side of the target knee (inner or outer).	

HP-5000 [REDACTED]	One patch applied [REDACTED] to alternate side of the target knee (inner or outer).	

Placebo	One patch applied [REDACTED] to alternate side of the target knee (inner or outer).	

	Treatment Arm	Treatment	HP-5000 [REDACTED]	One patch applied [REDACTED] to alternate side of the target knee (inner or outer).	HP-5000 [REDACTED]	One patch applied [REDACTED] to alternate side of the target knee (inner or outer).	Placebo	One patch applied [REDACTED] to alternate side of the target knee (inner or outer).
Treatment Arm	Treatment								
HP-5000 [REDACTED]	One patch applied [REDACTED] to alternate side of the target knee (inner or outer).								
HP-5000 [REDACTED]	One patch applied [REDACTED] to alternate side of the target knee (inner or outer).								
Placebo	One patch applied [REDACTED] to alternate side of the target knee (inner or outer).								
PLANNED STUDY SITES	Approximately [REDACTED] study sites in the United States.								
CRITERIA FOR EVALUATION OF STUDY OBJECTIVES	
Primary efficacy endpoint: The primary efficacy endpoint is the change in WOMAC LK3.1 OA pain score between Baseline and Week 4.
 
Secondary efficacy endpoints:
 
• WOMAC LK3.1 OA Index (pain) – change between Baseline and Week 1, and Week 2• WOMAC LK3.1 OA Index (stiffness) between Baseline and Week 1, Week 2, and Week 4• WOMAC LK3.1 OA Index (physical function) between Baseline and Week 1, Week 2, and Week 4• WOMAC LK3.1 OA Index (composite score) between Baseline and Week 1, Week 2, and Week 4• Patient Global Assessment between Baseline and Week 4• Patient Global Impression of Change between Week 1 and Week 4• Pain intensity assessed on an 11-point NRS between Baseline and Week 1, Week 2, and Week 4• Use of rescue medication between Baseline and Week 1, Week 2, and Week 4								

	
Safety endpoints:
 
• Adverse events, AEs leading to discontinuation from the study drug, SAEs, and deaths.• Change from Baseline in clinical laboratory results (including fasting glucose and total lipids [8 to 10 hours of fasting is required for these laboratory testing]), ECG results, body weight, and vital signs.• Dermal safety: adhesion, irritation, discomfort, and adhesive residue. 
Pharmacokinetic endpoint:
 
• Plasma concentrations of diclofenac (for both HP-5000 [REDACTED] and HP-5000 [REDACTED] on Day 14 and 28 (or at the Early Termination Visit).
STATISTICAL METHODS	
This section presents a summary of the planned statistical analyses. A Statistical Analysis Plan (SAP) that describes the details of the analyses to be conducted will be written prior to database lock. Unless otherwise indicated, all testing of statistical significance will be 2-sided. A difference resulting in a P value of <0.05 will be considered statistically significant.
 
For analyses involving study site, if the number of subjects per site is small, sites may be pooled for analysis, or omitted from statistical models. The final determination will be made prior to database lock.
 
Summary statistics will be provided for the variables described below. For continuous variables, these statistics will typically include the number of subjects, mean, standard deviation (SD), median, minimum, and maximum. For categorical variables, these statistics will typically include the number and percentage of subjects in each category.
 
Analysis Populations
 
• Intent-to-Treat (ITT): Will include all randomized subjects. Regardless of any protocol deviations, analyses performed on the ITT set will be based on the randomized treatment assignment and all available data.• Full Analysis Set (FAS): Will include all randomized subjects who have had at least 1 patch of Double-blind study drug applied and who have a Baseline WOMAC pain score and at least 1 post-baseline assessment of the primary efficacy measure (WOMAC pain score). Evaluable subjects will be defined as those who meet the FAS definition. The FAS will be used as the primary set for analysis of efficacy endpoints based on randomized treatment assignment.• Safety Analysis Set (SAF): Will include all subjects who have had at least 1 patch of double-blind study medication applied and who have at least 1 post-dose safety measurement during the Double-blind Treatment Phase. In the unlikely event that errors may have occurred in treatment arm assignments, then analyses using the SAF will be based on treatment actually received. The SAF will be used for both the analysis of dermal evaluations and safety endpoints.• Pharmacokinetic Analysis Set (PAS): Will include all subjects who have received at least 1 dose of study drug during the Double-blind Treatment Phase and have at least 1 blood sample for pharmacokinetic (PK) assessment. Subjects may be excluded from the PAS set if they significantly violate inclusion or exclusion criteria, significantly violate the protocol in a way that may influence the PK analysis, if any unexpected error occurs during the

study that may influence the PK analysis (e.g., early detachment of transdermal systems, apparent sample switching, etc.) or if their data are unavailable or incomplete. The PAS will be used for the analysis with model-based approach. Excluded cases will be documented together with the reason for exclusion.

Primary Efficacy Analysis: The primary efficacy endpoint of this study is the change from Baseline to Week 4 in the WOMAC pain score; the primary analysis set is the FAS. The comparisons of interest are:

- HP-5000 [REDACTED] versus placebo
- HP-5000 [REDACTED] versus placebo

The estimand in the primary analysis for efficacy for each dose is the difference between treatments groups (HP-5000 dose group *vs.* placebo) in the change from Baseline to Week 4 in WOMAC pain score in all subjects as randomized, under the assumption that all randomized subjects remain on their randomized treatment throughout the study. WOMAC scores obtained more than 24 hours after discontinuation of double-blind study drug will be excluded as a-priori defined outliers.

The primary efficacy variable, the change from Baseline to Week 4 in the WOMAC pain score will be analyzed using a mixed model repeated measures (MMRM) analysis. The MMRM model will include change from Baseline in WOMAC pain score as the repeated dependent variable, with treatment (HP-5000 [REDACTED], HP-5000 [REDACTED], and placebo), treatment-by-visit interaction, and the Baseline WOMAC pain score as covariates. An unstructured covariance matrix will be assumed. If the unstructured covariance matrix fails to converge, a series of other covariance structures will be tested for use. The MMRM model may be repeated on additional analysis sets as a sensitivity analysis. If the normality assumption is violated, analysis of covariance (ANCOVA) on rank-transformed data will be used as utility analysis and additional supportive analyses may be performed.

Other sensitivity analyses may be performed on the primary endpoint to assess the robustness of the results based on the model used for primary analysis. These analyses may include multiple imputation and pattern-mixture models for handling of missing data. Details will be provided in the SAP. The analyses will be performed according to the National Academy of Sciences (2010) guidelines.

Analysis of Secondary Efficacy Endpoints: Other secondary efficacy endpoints will be analyzed using the change in mean as appropriate.

- WOMAC LK3.1 OA Index (pain) – change between Baseline and Week 1, and Week 2.
- WOMAC LK3.1 OA Index (stiffness) between Baseline and Week 1, Week 2 and Week 4.
- WOMAC LK3.1 OA Index (physical function) between Baseline and Week 1, Week 2 and Week 4.
- WOMAC LK3.1 OA Index (composite score) between Baseline and Week 1, Week 2 and Week 4.
- Patient Global Assessment between Baseline and Week 4.
- Patient Global Impression of Change between Week 1 and Week 4.
- Pain intensity assessed on an 11-point NRS between Baseline, Week 1, Week 2, and Week 4.
- Use of rescue medication between Baseline and Week 1, Week 2 and Week 4.

	
Additional categorical response analyses may be performed; additional details will be provided in the SAP. Additional categorical response analyses may be performed; additional details will be provided in the SAP.
 
Analysis of Safety and Dermal Assessments: All safety summaries will be descriptive; statistical significance tests may be performed on safety data that will be described in the SAP. Safety variables include AEs, clinical laboratory values, vital signs, ECG readings, physical examination results, and dermal safety results. No formal inferential analyses will be conducted for safety variables, unless otherwise noted.
 
Analysis of PK: Plasma concentrations of diclofenac (for both HP-5000 [REDACTED] and HP-5000 [REDACTED] will be evaluated and summarized as descriptive statistics by treatment.

SAMPLE SIZE DETERMINATION	Assuming an effect size of [REDACTED] on the change in WOMAC pain score from Baseline to Week 4 between active HP-5000 [REDACTED] and HP-5000 [REDACTED] treatments vs. placebo, the probability for detecting the clinically meaningful effect size [REDACTED] or higher will be approximately 67% having 75 evaluable subjects per each active arm and 150 evaluable subjects in the placebo arm. Having 3 treatment arms, the total number of subjects randomized in the study and included in the primary analysis set should be approximately 300. A sufficient number of subjects will be screened to randomize the proposed sample size.
STUDY TREATMENT DURATION	The maximum treatment duration for each subject is 4 weeks. The total duration of study participation for each subject is approximately 9 weeks.

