(Day 0) will be calculated for subjects to be considered eligible for study participation and be randomized for study treatment (See **Section 8.2.1**). During the Washout Period, rescue medication (acetaminophen [APAP]) will be permitted (a maximum of 2 g/day) except within 2 calendar days prior to the Baseline Visit (i.e., rescue medication is prohibited from Day-2 until clinic visit on Day 0).

- **Baseline Visit:** Visit 2 (Day 0): Subjects will be re-evaluated according to the inclusion and exclusion criteria and the mean patient eDiary pain score will be calculated. Subjects who continue to meet all of the inclusion criteria, none of the exclusion criteria, who have completed the patient eDiary for **at least 2 daily NRS scores of the last 3 consecutive days immediately prior to the Baseline Visit**, and whose mean pain score is at least 5 at Baseline (V2) for those subjects who had a mean pain score of 2 to < 3 at the start of the Washout Period or has increased by at least 2 worsening scores for those who had a mean pain score of 3 to 6 at the start of the Washout Period and, will be randomized to receive one of 2 active formulations of HP-5000 or placebo (see **Section 8.2.1**).
- **Double-blind Treatment Phase:** On Day 1 of the Double-blind Treatment Phase, subjects will start applying their assigned patch for 4 consecutive weeks (from approximately Week 5 through 8): Subjects will be randomized to receive either HP-5000 [REDACTED] HP-5000 [REDACTED] or placebo patch. Dose modifications will **NOT** be permitted. Subjects who cannot tolerate their designated study drug dose will be withdrawn from the study.
- **Follow-up Period:** Visit 6 (Week 9): After the 4-week of the Double-blind Treatment Phase, the study center will conduct a follow-up phone call for safety monitoring or based on the investigator's judgment, a subject may return to the study center for the safety Follow-up Visit.

Note: All subjects will be contacted by phone between clinical visits to assess AEs, general well-being, provide visit reminders, and reinforce eDiary record and treatment compliance. Dose modifications will **NOT** be permitted and study procedures will be reinforced.

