10.1. Study Periods and Visits

10.1.1 Screening/Washout Period

10.1.1.1 Screening Period (Visit 1)

Screening/Washout Period should be up to 28 days prior to the Baseline Visit. The subject must be screened before entering the Washout Period of the study. The following procedures will be performed at Screening Visit (V1):

1. Obtain written informed consent and assign a screening number.
2. Assess inclusion/exclusion criteria.
3. Collect demographic information and record medical history, including prior and current therapies (e.g., prescription and nonprescription medications).
4. Perform a complete physical examination, which will include assessment of the head, eyes, ears, nose, and throat, cardiovascular, respiratory, gastrointestinal/abdominal, musculoskeletal, dermatological, neurological, and psychiatric/psychological body systems. Weight (kg), height (cm), and vital signs will be measured.
5. Perform urine drug, alcohol and pregnancy tests.
6. Identify the target knee. The subject will be instructed to refer to this specific (target) knee throughout his/her participation in the study when responding to study efficacy assessment.
7. Instruct the subject on how to use NRS and WOMAC before performing first assessments.
8. Administer the WOMAC questionnaire.
9. Perform NRS evaluation for the target knee and the non-target knee pain.
10. Review of X-ray of the target knee and perform 12-lead ECG and laboratory tests to determine subject's eligibility. If subject does NOT have any X-ray done within the past

year, a mandatory new X-ray to confirm the disease will have to be performed prior to starting the Washout Period.

[figure not shown]
11. Instruct the subject on how to use of an eDiary.
12. Dispense rescue medication.
13. Dispense an eDiary.

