13.2. Sample Size Determination

Assuming an effect size of [REDACTED] on the change in WOMAC pain score from Baseline to Week 4 between active HP-5000 [REDACTED] and HP-

5000 [REDACTED] treatments and placebo, the probability for detecting the clinically meaningful effect size [REDACTED] or higher will be approximately 67% having 75 evaluable subjects per each active arm and 150 evaluable subjects in the placebo arm. Having 3 treatment arms, the total number of subjects randomized in the study and included in the primary analysis set should be approximately 300. A sufficient number of subjects will be screened to randomize the proposed sample size.

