13.4. Statistical Analyses

This section presents a summary of the planned statistical analyses. A Statistical Analysis Plan (SAP) that describes the details of the analyses to be conducted will be written prior to database lock. Unless otherwise indicated, all testing of statistical significance will be 2-sided, and a difference resulting in a P value of <0.05 will be considered statistically significant. For analyses involving study site, if the number of subjects per site is small, sites may be pooled for analysis, or omitted from statistical models. The final determination will be made prior to database lock.

Summary statistics will be provided for the variables described below. For continuous variables, these statistical analyses will typically include the number of subjects, mean, standard deviation (SD), median, minimum, and maximum. For categorical variables, these statistics will typically include the number and percentage of subjects in each category.

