5.1.2. Adjustments for Covariates

Additional covariates for exploration include BMI, and Gender which may be added to analyses beyond baseline covariate factors, and will be noted in table outputs as appropriate. Further exploration of additional covariates will be considered as data becomes available and may

AD-ST-33.04 Effective date: 30-Jun-2017

include subgroups described in section [5.1.8](#).

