5.1.3. Multiple Comparisons/Multiplicity

There will be no adjustments for multiple comparisons for efficacy or safety endpoints.

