7.1. Primary Efficacy Analysis

The estimand in the primary analysis for efficacy for each dose is the difference between treatments groups (each HP-5000 treatment group vs. placebo) in the change from Baseline to Week 4 in WOMAC pain score in all subjects as randomized, under the assumption that all randomized patients remain on their randomized treatment throughout the trial.

AD-ST-33.04 Effective date: 30-Jun-2017

Version 1.0 | Date 21-Oct-2019 | AD-PR-109.01 Effective date: 26-Jun-2017

Page 24 of 124

Statistical Analysis Plan,
 Sponsor Noven Pharmaceuticals, Inc.
 Protocol Number HP-5000-US-05
 [REDACTED]

The comparisons of interest are:

- HP-5000 [REDACTED] versus placebo
- HP-5000 [REDACTED] versus placebo

WOMAC scores obtained 24 hours after removal/detachment of the study medication or WOMAC scores obtained within 24 the subject used rescue medication will be excluded as outliers. Outliers will be defined *a priori* as (i) WOMAC scores obtained more than 24 hours after removal/detachment of double-blind study medication; or (ii) WOMAC scores obtained within 24 hours the subject used rescue medication.

The change from Baseline to Week 4 in the WOMAC pain score will be analyzed using a mixed model repeated measures (MMRM) analysis. The MMRM model will include change from baseline in WOMAC pain score as the repeated dependent variable, with treatment (HP-5000-[REDACTED], HP-5000-[REDACTED], and placebo), visit, treatment-by-visit interaction, and the baseline WOMAC pain score as covariates. The mean difference of change will be compared for each active treatment arm, and overall active against placebo. An unstructured covariance matrix will be assumed. If the unstructured matrix fails to converge, a series of other covariance structures will be tested (AR(1), Toeplitz, and Compound Symmetry). The covariance structure which converges with the lowest Akaike information criterion (AIC) score will be chosen and noted in the resulting table. The Kenward-Roger approximation for denominator degrees of freedom will be implemented, and the restricted maximum likelihood (REML) approach for estimation will be specified in the model code.

Below is example SAS code for conducting the MMRM analysis specified. Note, the macro wrapper used in different covariance structures is not shown below (specified with type option):

[figure not shown]
[figure not shown]
[figure not shown]
```
ods output lsmeans = lsmn1
      lsmestimates = lsmest1

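### Optional precision gain: the primary MMRM could also adjust for the pre-randomisation target-knee diary NRS mean, which the plan requires but uses only for subgroups and possible exploration

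*Protocol*

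**What the plan says.** **Primary model.** The protocol synopsis lists "treatment-by-visit interaction, and the Baseline WOMAC pain score as covariates" among the model terms. Protocol 13.4.3.1 has the same single baseline covariate, and SAP 7.1 gives "visit, treatment-by-visit interaction, and the baseline WOMAC pain score as covariates". In the SAP code the only baseline term is the baseline value of the score being analysed. SAP 5.1.1 defines baseline as one observation, normally the Baseline Visit value.

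**Diary NRS.** Protocol 7.1 (Baseline Visit) makes randomisation conditional on "at least 2 daily NRS scores of the last 3 consecutive days immediately prior to the Baseline Visit", and calculates a mean from them.

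**Screening WOMAC.** Protocol 10.1.1.1 includes the step "Administer the WOMAC questionnaire" at Visit 1.

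**Other covariates.** SAP 5.1.2 says "Additional covariates for exploration include BMI, and Gender which may be added to analyses". It goes on to allow further exploratory covariates, which may come from the subgroup list in SAP 5.1.8. That list includes baseline NRS severity in two classes, 5 to 6 and 7 or more.

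**Testing and power.** Under Protocol 13.4, "all testing of statistical significance will be 2-sided, and a difference resulting in a P value of <0.05 will be considered statistically significant". SAP 5.1.3 adds: "There will be no adjustments for multiple comparisons for efficacy or safety endpoints". Protocol 13.2 states that the probability of detecting the effect "will be approximately 67% having 75 evaluable subjects per each active arm and 150 evaluable subjects in the placebo arm".

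**The concern.** The primary model uses one five-item score from one visit, whose range is cut by an entry threshold (inclusion 5, value redacted). A multi-day measure of pain in the same knee, fixed before treatment, exists by design for every properly randomised subject. Splitting it into two classes for subgroup work, or leaving it for exploration once data are available, gives up whatever it would add to the primary comparison as a continuous covariate.

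The stake is modest but real. Stated power is only about 67% for each formulation against placebo, and SAP 3.2 accepts a fall to as low as 40% if enrolment is short. SAP section 2 says that the study feeds the choice of what advances to phase III, so a narrower interval at almost no cost is worth having.

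**Working it through.** **1. The plan's own figure.** The current protocol and the SAP redact the effect size. A value of 0.32 is legible only in the synopsis of a superseded protocol version in the same file. With 75 v 150 subjects and two-sided 0.05:

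- 0.32 / sqrt(1/75 + 1/150) = 2.263
- Power = Phi(2.263 - 1.96) = 61.9%

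This does not reproduce 67%, which would need an effect size of about 0.339. The gap is not called an error. The threshold in the protocol's sentence is redacted, and 67% would also be the probability of observing about 0.26 or more if the true effect is 0.32. Below, 67% is taken at face value as conventional power, so the expected test statistic is 1.96 + 0.44 = 2.40.

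**2. Assumed inputs (none in the documents).**

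- a, Week 4 WOMAC pain with Baseline WOMAC pain: 0.3-0.5
- b, Week 4 WOMAC pain with the diary NRS mean: 0.25-0.45
- c, the two baseline measures with each other: 0.4-0.7

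**3. Formulas.** The check treats Week 4 as a single analysis of covariance. With baseline in the model, analysing the change or the Week 4 score gives the same treatment difference.

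- R2 with Baseline WOMAC only = a^2
- R2 with both = (a^2 + b^2 - 2abc) / (1 - c^2)
- Residual variance ratio f = (1 - R2 both) / (1 - a^2)
- Power = Phi(2.40 / sqrt(f) - 1.96)
- Equivalent total sample = 300 / f

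**4. Worked example, a = 0.4, c = 0.55.** Here 1 - a^2 = 0.84 and 1 - c^2 = 0.6975.

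| b | R2 both | f | Variance cut | Power | Equivalent N |
|---|---|---|---|---|---|
| 0.25 | 0.1613 | 0.9985 | 0.15% | 67.1% | about 300 |
| 0.35 | 0.1842 | 0.971 | 2.9% | 68.3% | about 309 |
| 0.45 | 0.2358 | 0.910 | 9.0% | 71.1% | about 330 |

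**5. Whole grid.** f runs from 0.858 to 1.000, a variance cut of 0-14% and power of 67-74%. The median over an evenly spaced grid is a cut of about 2.9% and power of 68.3%. The best corner (a = 0.3, b = 0.45, c = 0.4) needs the NRS to predict Week 4 WOMAC better than WOMAC itself does. Requiring b to be no larger than a, the median cut is 1.8% and median power 67.8%.

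**6. NRS mean and Screening WOMAC together.** Four assumed correlation sets gave partial R2 of 0.006, 0.02, 0.05 and 0.15, worth about 0.2, 0.9, 2.3 and 7 percentage points of power.

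**The case against.** The strongest reply is that adjusting for the endpoint's own baseline is coherent and pre-specified, and that a second pain covariate is a preference. Several parts of this stand.

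- **The NRS is not ignored.** A reader who stops at BMI and gender in SAP 5.1.2 might infer that it is. The same paragraph opens exploration to the SAP 5.1.8 factors, which include baseline NRS severity. What is missing is a continuous, pre-specified role in the primary model.
- **The NRS mean is range-restricted too.** Protocol 7.1 requires at least 5 for subjects starting at 2 to below 3, and a rise of at least 2 for those starting at 3 to 6. Either route gives 5 or more on a 0-10 scale, which may weaken its correlation with Week 4 pain.
- **Screening WOMAC is a weaker candidate.** It is taken before washout, in subjects on stable NSAID therapy, so it describes a different pain state and may add little.
- **Subjects could be lost.** The FAS requires a Baseline WOMAC pain score and one post-baseline score, not an NRS mean. PROC MIXED drops records with a missing covariate, so a rule is needed.
- **The covariate is not yet defined.** Protocol 10.2.1.4 collects both average and worst pain, and its three-day averaging note excludes Baseline. Two bullets of Protocol 7.1 give different day rules. SAP 5.1.6 averages over both knees.
- **Imputation must match.** The Method 2 code in SAP 7.1.1 uses only treatment, baseline and the scores.

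None of this removes the point. It lowers the expected gain and sets out what a usable specification must contain.

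**Conclusion.** The point holds as an optional, low-cost improvement. Baseline WOMAC pain is the only baseline covariate in every statement of the primary MMRM, while a pre-randomisation NRS mean is required by design and is left to subgroup and exploratory use.

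The size is an assumed range: a residual variance cut of 0-14%, typically about 3%. With 67% read as conventional power, that gives 67-74%, typically about 68%. Range restriction may put the true gain near the bottom.

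Two stronger inferences are not supported. The first is that the primary analysis is wrong or biased: the single-covariate model is a valid comparison of the same estimand. The second is that the change would repair the study's power: the documents contain no correlation to justify that, and the upper end of the range rests on the least plausible combination of assumptions.

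**What to change.** Before unblinding, amend Protocol 13.4.3.1, SAP 7.1 and the code as follows.

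1. **Add one continuous covariate to the primary MMRM.** Use the mean target-knee diary NRS for average pain over the past 24 hours, taken over the available days (at least 2) of the last 3 days before the Baseline Visit. Do not use the two-knee average in SAP 5.1.6.
2. **Fill any missing value with the overall mean, blind to arm**, so that no FAS subject is dropped.
3. **Include the same covariate in the Method 1 and Method 2 imputation models** (SAP 7.1.1) and in the MMRM fitted after imputation.
4. **Keep the current single-covariate model as a supportive analysis.**
5. **Treat Screening WOMAC pain as optional only.**

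The cost is about one degree of freedom out of roughly 300 subjects and minor programming. No new data are needed.
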